## **Type of Units Assigned**

### **Period(s)**

The duration of the trial is 38 weeks for each patient, including a 2-week baseline assessment (week 0-2), 12-week treatment period (week 1-12), and 24-week follow-up (week 13-36).

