### **3. Outcome Measures**

#### **Primary outcome**

The primary outcome in this trial is the change in the average of VAS-BP scores in the first 2 weeks of menstruation, recorded in the patient daily diary.

The VAS-BP will be measured using a 10cm linear VAS with 0 representing no pain and 10 the worst imaginable pain from baseline at weeks 4, 8, and 12.

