### **Statistical analysis**

Sample size estimation was based on changes in the breast pain VAS(VAS-BP) score. According to the pre-trial, the VAS-BP score significantly decreased by  $2.98 \pm 0.95$  in MA group compared to  $2.35 \pm 0.97$  in the SM group after treatment from baseline. In the current trial, we assume a significance level  $\alpha = 0.05$  and power  $(1-\beta) = 0.90$ , and providing for a two-sided outcome, at least 42 participants will be required for each group, as calculated by PASS version 11.0 (NCSS, LLC, Kaysville, UT, USA), assuming a two-tailed test with a 20% drop-out rate, a total of 108 patients (54 in each group) will be recruited.

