#### Statistical methods

##### Statistical methods for primary and secondary outcomes

We will use SPSS 22.0 software (IBM SPSS Statistics; IBM Corp, Somers, NY) to perform all statistical analyses following the intention-to-treat principle. The CI will be established at 95%, and the significance level at 0.05. For continuous data, the data will be presented as mean  $\pm$  standard deviation when normally distributed or presented as median (IQR) when not normally distributed. Statistical comparisons will be performed by the independent-sample t tests or Wilcoxon rank-sum test for continuous data and by X-test or Fisher exact test for categorical data, as appropriate. A p-value  $< 0.05$  will be considered statistically significant.

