##### Methods for additional analyses (e.g. subgroup analyses)

Not applicable.

Methods in analysis to handle protocol non-adherence and any statistical methods to handle missing data

We perform statistical analysis on complete case. The researcher will contact participants as much as possible to supplement missing data. The missing data will be assessed using an intention-to-treat analysis.

Plans to give access to the full protocol, participant level-data and statistical code

The data sharing will be available upon request and with permission and

approval from the Pinggu Hospital of Beijing Traditional Chinese medicine hospital.

[figure not shown]

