#### 5. Results Point of Contact

[name], Chief physician, Department of Acupuncture and Moxibustion, Beijing Pinggu District Hospital of Traditional Chinese Medicine, 101200, Beijing, China.[name], [[contact]](mailto:[contact])

Figure 1. Flow chart of participants through the proposed trial.

The schedule of the whole procedure is shown in Table1

Table1 Study period.

	STUDY PERIOD						
	Enrolment	Allocation	Treatment			Follow up	
Timepoint(W,week)	-2	0	4	8	12	24	36
ENROLMENT							
Eligibility screen	X						
Informed consent	X						
Allocation		X					
Interventions							
Manual acupuncture			◆—————◆				
Sham acupuncture			◆—————◆				
Assessment							
VAS-BP	X	X	X	X	X	X	X
NDBP	X	X	X	X	X	X	X
WHOQOL-BREF		X			X		
Breast glandular thickness		X			X		
Breast duct width		X			X		
Patients' global improvement assessment					X		
Patients'acceptability			X		X		
Blindness assessment					X		
Safety assessment			X	X	X	X	X

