## Statistical Analysis Plan

Statistical methods for primary and secondary outcomes

We will use SPSS 22.0 software (IBM SPSS Statistics; IBM Corp, Somers, NY) to perform all statistical analyses following the intention-to-treat principle. The CI will be established at 95%, and the significance level at 0.05. For continuous data, the data will be presented as mean  $\pm$  standard deviation when normally distributed or presented as median (IQR) when not normally distributed. Statistical comparisons will be performed by the independent-sample t tests or Wilcoxon rank-sum test for continuous data and by X-test or Fisher exact test for categorical data, as appropriate. A p-value  $<0.05$  will be considered statistically significant.

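### The primary outcome is listed at weeks 4, 8 and 12 with no deciding visit, pooled contrast or multiplicity rule; if any significant visit may count, the two-sided false positive rate is about 8–13% (assumed between-visit correlation 0.9 to 0.5), not 5%.

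*Combined protocol and SAP*

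**What the plan says.** Section 3 of the protocol, under Primary outcome, defines one quantity: "The primary outcome in this trial is the change in the average of VAS-BP scores in the first 2 weeks of menstruation". The average is taken over diary scores within a two-week window; nothing says that it runs across visits. The next sentence describes the scale and ends "worst imaginable pain from baseline at weeks 4, 8, and 12".

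The analysis text is the same in the protocol (Statistical methods for primary and secondary outcomes) and in the SAP. On error control it says: "The CI will be established at 95%, and the significance level at 0.05". On method it says: "Statistical comparisons will be performed by the independent-sample t tests or Wilcoxon rank-sum test for continuous data". It gives no repeated-measures model, testing order, pooled contrast or multiplicity adjustment. The section on additional analyses is marked as not applicable and adds nothing on this point.

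Three other places bear on the intended visit:

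- The sample size paragraph (Statistical analysis) uses one pair of mean changes, the sham figure being that "in the SM group after treatment from baseline". It names no week.
- Period(s) ends the treatment phase at week 12.
- Table 1 schedules VAS-BP at weeks 4, 8, 12, 24 and 36 during and after treatment and marks none as primary. Weeks 24 and 36 are absent from the primary outcome text and are not counted here.

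**The concern.** A two-group test needs one value per patient. Three analyses fit the text equally well: the week-12 change alone, the mean change over the three visits, or a separate test at each visit. Two analysts could follow the plan faithfully, pick different ones and reach opposite conclusions from the same data.

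The trial's one confirmatory claim rests on this outcome. If the choice is left open until results are known, the stated 0.05 no longer describes the chance of a false claim. With three candidate tests and no rule, a reader of the final report could not tell whether a significant week-8 result, say, was the planned test or the most favourable one.

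**Working it through.** **Inputs.** Three visits (Primary outcome). Level 0.05 (protocol statistical methods and SAP), two-sided (sample size paragraph). 54 per group recruited, or 54 × 0.80 = 43.2, about 43, after the planned 20% drop-out. The correlation between visits is not in the documents and is assumed.

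**1. The plan's own figure.** One test at week 12 should give 5%. In simulated t-tests on change scores (60,000 trials per setting) it gave 4.9–5.2%. One test of the average over the three visits gave 5.0% at every correlation tried. The stated 0.05 is right if there is one prespecified test.

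**2. Upper reference.** Three independent tests: 1 − 0.95³ = 0.1426, or 14.3%.

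**3. What correlation is plausible?** The three changes come from the same patients and share one baseline. Let all raw scores have correlation r, and let k be the ratio of follow-up SD to baseline SD. The correlation between two change scores is then

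ρ = (1 − 2kr + k²r) / (1 + k² − 2kr).

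- k = 1: ρ = (1 − r)/(2 − 2r) = 0.50, whatever r is.
- k = 0.7, r = 0.5: 0.545/0.79 = 0.69.
- k = 0.5, r = 0.5: 0.625/0.75 = 0.83.

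A range of 0.5 to 0.9 is therefore reasonable; 0.95 is shown as an extreme.

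**4. Error if any visit may count.** For three null statistics with common correlation ρ and c = 1.96,

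P(any |Z| > c) = 1 − ∫ φ(u) [Φ((c − √ρ·u)/√(1−ρ)) − Φ((−c − √ρ·u)/√(1−ρ))]³ du.

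The column for results favouring manual acupuncture (MA) drops the second Φ term. The Bonferroni column tests each visit at 0.05/3.

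| Assumed ρ | Two-sided, any visit | Favouring MA (nominal 2.5%) | Bonferroni, two-sided |
|---|---|---|---|
| 0.5 | 12.5% | 6.3% | 4.5% |
| 0.6 | 11.8% | 5.9% | 4.2% |
| 0.7 | 10.9% | 5.5% | 3.9% |
| 0.8 | 9.8% | 4.9% | 3.5% |
| 0.9 | 8.4% | 4.2% | 3.0% |
| 0.95 | 7.3% | 3.7% | 2.6% |

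**5. Sensitivity.** If the correlation decays with time (adjacent visits r, weeks 4 and 12 r²), the two-sided error is 12.9% at r = 0.5, 11.4% at 0.7, 10.3% at 0.8 and 8.8% at 0.9. Simulated t-tests with 43 or 54 per group and a shared baseline gave 12.6–12.8% for k = 1, 10.6–11.1% for k = 0.7 and 8.8–9.6% for k = 0.5. Small-sample behaviour does not change the picture.

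**6. What adjustment would cost.** Take the plan's difference, 2.98 − 2.35 = 0.63, and pooled SD √((0.95² + 0.97²)/2) = 0.960. By the normal formula, 43 per group gives about 86% power for one test at 0.05 and about 74% at 0.05/3. Reaching 90% power at 0.05/3 would need 63 per group.

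**The case against.** The strongest reply is that week 12 is already the natural reading. The defining sentence is singular. The sentence with the weeks opens by describing how VAS-BP is measured, so it can be taken as a visit schedule. Treatment ends at week 12, the sample size covers one after-treatment contrast at one 0.05, and quality of life, ultrasound and global improvement are all assessed at week 12 only. On this view the plan lacks a sentence, not an analysis.

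That makes week 12 the probable intent, and it supports the choice of fix. It does not settle the matter. Under Secondary outcomes the authors gave quality of life and ultrasound a single week 12, but listed the number of breast pain days at weeks 4, 8 and 12, as they did for the primary outcome. They drew the distinction where they wanted it, so week 12 cannot simply be read into the primary outcome. An inferred intent also does not bind the analyst.

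A second reply is that the error figures depend on an any-visit rule found nowhere in the documents. This is correct. The silence covers conservative rules too: if all three visits had to be significant, the error would not exceed 5%, though power would no longer be that of the single contrast in the sample size paragraph. The figures show what the plan leaves possible; they are not its established error rate.

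**Conclusion.** The concern holds. Without any assumption, the primary comparison is not identified: up to three unadjusted tests fit the text, and the deciding one can be picked afterwards. This should be fixed before the data are analysed.

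The size depends on two assumptions: that significance at any visit counts, and that the between-visit correlation lies between 0.5 and 0.9. The two-sided false positive rate is then about 8–13% against the stated 5%, and false positives favouring manual acupuncture are 4.2–6.3% against a nominal 2.5%. Even at a correlation of 0.95 the two-sided rate is 7.3%, about one and a half times the stated level.

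**What to change.** State in Primary outcome, in the protocol's statistical methods and in the SAP that the single primary comparison is the difference between the manual and sham groups in change in VAS-BP from baseline at week 12, tested at two-sided 0.05. Make weeks 4 and 8 secondary, reported with confidence intervals. Add to the sample size paragraph that its figures refer to the week-12 comparison.

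A fixed testing order starting at week 12 would also hold 5%, as would one prespecified pooled or repeated-measures contrast. If a pooled contrast is preferred, the after-treatment means and SDs behind the sample size must be restated for it. Bonferroni is valid but costs power, as shown above. Week 12 is suggested because it fits the end of treatment and the existing sample size contrast.

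The cost is one sentence in each of the four places, with no extra patients or visits. The sponsor gives up the option of claiming weeks 4 or 8 as primary results. The same edit should say which cycle's diary days supply the week-12 value; that definition may need more than a sentence.

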#### **Secondary outcomes**

1. The changes in the number of nominal days of breast pain (NDBP) during 2 weeks before menstruation from baseline at weeks 4, 8, 12.

2. The changes of WHOQOL-BREF scores from baseline at weeks 12. The

WHOQOL-BREF china version will be used to evaluate the QOL of the participants. The WHOQOL-BREF Questionnaire consists of 26 items, in which the first and second questions of the questionnaire are about the QOL and health status in general. The next 24 questions assess the QOL in four dimensions: physical health (7 items); psychological (6 items); environment (8 items); and social relationships (3 items). Each item is answered on a five-point scale. A higher score denotes a better quality of life [3-4].

3. The changes in breast glandular section thickness, and breast duct width three days before menstruation from baseline at weeks 12.

Mammary ultrasonography will be used to observe breast glandular section thickness, and breast duct width. All ultrasound image acquisition work is completed by the same ultrasound physician with at least 5 years of professional practice.

4. Patients' global improvement assessment: It will be assessed by a 7-point self-reporting scale ranging from 1 to 7: significantly reduced, moderately reduced, slightly reduced, no change, slightly aggravated, moderately aggravated, and significantly aggravated. The proportion of patients reporting "significantly reduced" or "moderately reduced" is recorded as the response rate of overall efficacy.

5. Patients' acceptability toward acupuncture at the end of the 1st treatment at week 1 and the last treatment at week 12. The acceptability of acupuncture will be assessed among participants in the MA group using a 3-point index: unacceptable (0 points), acceptable (1 point), and easy to accept (2 points). Those who regard acupuncture as unacceptable will report the reasons. The average score will be calculated after the 2

assessments.

6. Blindness assessment: within 3 min after the last treatment session at week 12, all participants will be asked to answer the question do you think you have received acupuncture treatment and choose the answer between the options of Yes or No.

### **Statistical analysis**

Sample size estimation was based on changes in the breast pain VAS(VAS-BP) score. According to the pre-trial, the VAS-BP score significantly decreased by  $2.98 \pm 0.95$  in MA group compared to  $2.35 \pm 0.97$  in the SM group after treatment from baseline. In the current trial, we assume a significance level  $\alpha = 0.05$  and power  $(1-\beta) = 0.90$ , and providing for a two-sided outcome, at least 42 participants will be required for each group, as calculated by PASS version 11.0 (NCSS, LLC, Kaysville, UT, USA), assuming a two-tailed test with a 20% drop-out rate, a total of 108 patients (54 in each group) will be recruited.

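### The sample size of 42 per group does not deliver the stated 90% power: the plan's own inputs require 50 per group, and 42 gives about 84%.

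*Combined protocol and SAP*

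**What the plan says.** The protocol's Statistical analysis section sizes the trial on the primary measure: "Sample size estimation was based on changes in the breast pain VAS(VAS-BP) score". From a pre-trial it takes mean decreases of 2.98 (SD 0.95) in the manual acupuncture group and 2.35 (SD 0.97) in the sham group. Alpha is 0.05 and power 0.90. The test is described as two-sided twice in the same sentence, first as "providing for a two-sided outcome" and then as "assuming a two-tailed test with a 20% drop-out rate". The result, attributed to PASS 11.0, is that "at least 42 participants will be required for each group". The paragraph then moves to the recruited number: "assuming a two-tailed test with a 20% drop-out rate, a total of 108 patients (54 in each group) will be recruited". Allocation is 1:1 (Arm/Group Title).

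For the analysis, the protocol section on primary and secondary outcomes and the SAP carry the same sentence: "Statistical comparisons will be performed by the independent-sample t tests or Wilcoxon rank-sum test for continuous data". Neither describes covariate adjustment or a repeated-measures model. On missing data, the protocol states "We perform statistical analysis on complete case", and adds that missing data will be assessed by intention to treat, without naming a method.

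**The concern.** The standardised difference implied by the inputs is about 0.66. At two-sided 5% and 90% power, an effect of that size needs close to 50 per group, so 42 looks too small by about eight per group. All the inputs are printed, so anyone can repeat the calculation and see that inputs and result cannot all be right.

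What is at stake is how a null result is read. If the trial finds no difference, it will be presented as a 90%-powered study, when at the plan's own drop-out rate the chance of missing a true difference of 0.63 is about 15%. The drop-out allowance is meant to protect the stated power at that loss, and here it does not.

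**Working it through.** **Inputs** (all from the protocol)

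- Difference in mean change: 2.98 − 2.35 = 0.63.
- Pooled SD: √[(0.95² + 0.97²)/2] = √(1.8434/2) = 0.960.
- Standardised effect: d = 0.63/0.960 = 0.656.
- Two-sided alpha 0.05, power 0.90, 1:1 allocation, 20% drop-out.

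**Attempt to reproduce 42**

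Normal approximation:

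n = (z₀.₉₇₅ + z₀.₉₀)² × (SD₁² + SD₂²) / difference² = (1.960 + 1.2816)² × 1.8434 / 0.63² = 48.8, so 49 per group.

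The t-test calculation uses the noncentral t distribution with 2n − 2 degrees of freedom and noncentrality d√(n/2). Power is 0.895 at n = 49 and 0.901 at n = 50, so 50 per group are needed. Using SD 0.95 throughout gives 49, and SD 0.97 gives 51. The stated 42 is not reproduced by any of these.

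**Power at the planned numbers** (two-sided t-test)

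| Evaluable per group | Power |
|---|---|
| 42 | 84.4% |
| 43 | 85.3% |
| 49 | 89.5% |
| 50 | 90.1% |
| 54 | 92.2% |

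At n = 42 the noncentrality is 0.656 × √21 = 3.01 and the critical value is 1.989, which gives the 84.4%. The Welch form with unequal SDs gives the same figure. Simulation of the t-test (40,000 runs) gives 0.844, 0.854, 0.902 and 0.921 at 42, 43, 50 and 54.

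**Drop-out**

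42/0.8 = 52.5, so 53; the planned 54 covers that. Going the other way, 54 × 0.8 = 43.2. Power by loss from 54 per group:

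| Loss | Evaluable per group | Power |
|---|---|---|
| 0% | 54.0 | 92.2% |
| 5% | 51.3 | 90.9% |
| 10% | 48.6 | 89.3% |
| 15% | 45.9 | 87.5% |
| 20% | 43.2 | 85.4% |

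Fifty completers out of 54 is a loss of 4/54 = 7.4%, so 90% holds only up to about 7% loss.

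**Could rounding explain it?**

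Taking the difference as 0.64 and the SDs as 0.945 and 0.965, the requirement is still 48, and 42 gives 85.9%. The least favourable rounding (0.62; 0.955 and 0.975) needs 52, and 42 gives 82.9%.

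**Could different inputs explain it?**

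Two nearby calculations come close to 42:

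- Two-sided alpha 0.05 with 85% power: 41.7, so 42, by the normal approximation; 43 by the t-test.
- One-sided alpha 0.05 with 90% power: 39.8, so 40, by the normal approximation; 41 by the t-test.

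Each contradicts something the paragraph states. The documents do not show which calculation was run.

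**What 90% would require**

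50/0.8 = 62.5, so 63 randomised per group, 126 in total. Alternatively, with 43 per group and SD 0.96, 90% power needs a true difference of 0.68 rather than 0.63.

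**The case against.** The best defence is that 54 per group are randomised, not 42. With little loss the trial does exceed 90% power, and the shortfall at the planned loss is only 5 to 6 points on a figure that rests on pre-trial estimates. That is a fair statement of scale. It does not rescue the claim, because the 20% loss is the plan's own assumption and 90% is lost once attrition passes about 7%.

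A second point is that the missing-data text is not consistently complete-case: it also invokes intention to treat. The figure of about 43 analysed does rest on the complete-case reading. But no method is named that would bring those lost to follow-up into the analysis, and a label alone does not replace outcome data that were not collected.

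A third is that the rank-sum test might be used instead. If the data were normal, it would lower power slightly (about 82% at 42 and 84% at 43 by simulation). With heavy-tailed data it could do better than the t-test. The plan gives no distribution, so this neither supports nor repairs the 42.

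Finally, the source of 42 cannot be established from the documents. That stands, and it is a reason to consult the PASS output rather than to presume a particular slip.

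**Conclusion.** The concern holds. On the stated difference, SDs, two-sided alpha and power, 50 per group are required by the t-test (49 by the normal approximation). The stated 42 gives 84.4%, and the roughly 43 left after the planned loss give 85.3%. This rests on an unadjusted comparison at a single time point, approximately normal changes, and analysis of those with outcome data. No choice of formula, SD or rounding that keeps the stated inputs brings the requirement below 48. The consequence is confined to the power claim and the reading of a null result. Even so, the claim justifies the size of the trial on its primary outcome and should be corrected.

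**What to change.** Retrieve the PASS output and check its procedure and inputs against the text. Then take one of two routes.

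1. **Keep 108 and restate the power.** For example: *With 108 randomised (54 per group) and 20% drop-out, about 43 per group will be evaluable, giving about 85% power to detect a difference of 0.63 (SD about 0.96) in change in VAS-BP with a two-sided t-test at alpha 0.05.* The sentence should also name the time point it refers to, since the outcome section lists weeks 4, 8 and 12. The cost is one sentence and a less favourable stated power; no further patients are needed.
2. **Keep 90% with the present unadjusted test.** This needs 50 completers, or 63 randomised, per group: 126 in total, 126 − 108 = 18 more patients. The choice is the sponsor's.

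A baseline-adjusted primary analysis (ANCOVA) is optional and may recover some power at the same size, but it should not be relied on without stated assumptions. The gain depends on the baseline to follow-up correlation r and on the ratio of follow-up to baseline SD, neither of which the documents give. At 43 per group, with the change-score SD held at 0.96, power would be:

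| Follow-up SD / baseline SD | r = 0.5 | r = 0.72 |
|---|---|---|
| 0.8 | about 98% | about 97% |
| 1 | about 93% | about 90% |
| 1.25 | about 89% | about 86% |

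The last of these is almost no gain on 85.3%.

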#### Data management

The clinical trial management platform ResMan will be used to manage the data. Repeated input methods will be used to ensure that the entered data is correct. The database will be locked with a password, which will only be known by relevant personnel.

#### Statistical methods

##### Statistical methods for primary and secondary outcomes

We will use SPSS 22.0 software (IBM SPSS Statistics; IBM Corp, Somers, NY) to perform all statistical analyses following the intention-to-treat principle. The CI will be established at 95%, and the significance level at 0.05. For continuous data, the data will be presented as mean  $\pm$  standard deviation when normally distributed or presented as median (IQR) when not normally distributed. Statistical comparisons will be performed by the independent-sample t tests or Wilcoxon rank-sum test for continuous data and by X-test or Fisher exact test for categorical data, as appropriate. A p-value  $< 0.05$  will be considered statistically significant.

